Assuming about a 15% drop out rate, the sample size will be approximately 100 evaluable subjects total across the placebo groups and approximately 50 subjects in each of six ALN-PCSSC dose groups. This sample size of at least 400 evaluable subjects will provide more than 90% power to detect a 30% reduction of LDL-C levels in at least one ALN-PCSSC dose group.

Primary Endpoint Analysis:

Two sample t-tests will be performed to test the superiority of any dosing group over placebo. A Dunnet multiple t-test procedure will be applied to adjust for multiple comparisons with six different dosing regimens.

Secondary and Exploratory Endpoint Analysis:

The analysis of the secondary and exploratory endpoints will be descriptive.

Interim Analysis:

An interim analysis of lipids and PCSK9, unblinded by dose cohort only, will be prepared upon completion of Day 90 by the Statistical Reporting Organization. The interim analysis will be performed for all subjects completing Day 90 and these data will be used to help select the ALN-PCSSC dose for subsequent clinical trials.

TABLE OF CONTENTS

PROTOCOL SYNOPSIS	3
LIST OF ABBREVIATIONS	13
1. INTRODUCTION	15
1.1. Background	15
1.1.1. Disease Overview	15
1.1.2. PCSK9 Biology and Target Rationale	15
1.1.3. Mechanism of RNA Interference	16
1.2. ALN-PCSSC, an RNAi Therapeutic for Hypercholesterolemia	17
1.2.1. Preclinical Studies	17
1.2.2. Clinical Studies	18
1.2.3. Known and Potential Risks and Benefits	18
1.3. Study Rationale	19
1.3.1. Study Rationale	19
1.3.2. Dose Rationale	19
1.4. Study Population	19
2. TRIAL OBJECTIVES AND PURPOSE	20
2.1. Primary Objective	20
2.2. Secondary Objectives	20
2.3. Exploratory Objectives	20
3. TRIAL DESIGN	21
3.1. Type/Design of Trial	21
3.2. Schematic Diagram of Trial Design	22
3.2.1. One Dose (one or two injections on Day 1)	22
3.2.2. Two Doses (one injection each on Day 1 and Day 90)	23
3.3. Primary Endpoint(s)	23
3.4. Secondary Endpoints	23
3.5. Exploratory Endpoint(s)	24
3.6. Measures to Minimize/Avoid Bias	24
3.6.1. Blinded Study Where Pharmacist is Unblinded	24
4. SUBJECT POPULATION	25
4.1. Number of Subjects	25

4.2.	Inclusion Criteria	25
4.3.	Exclusion Criteria	25
4.4.	Withdrawal Criteria	27
4.4.1.	Withdrawal from Study Medication	28
5.	TREATMENT OF SUBJECTS	29
5.1.	Study Medications	29
5.1.1.	ALN-PCSSC	29
5.1.2.	Placebo	29
5.1.3.	Packaging and Labeling	29
5.1.4.	Storage	29
5.1.5.	Accountability	29
5.2.	Concomitant Medications	30
5.2.1.	Prohibited Concomitant Medications	30

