3.4. Secondary Endpoints

The secondary endpoints of this trial are:

- Percentage change in LDL-C from baseline to Day 90
- Percentage change in LDL-C from baseline to Days 14, 30, 60, 104, 120, 150, and 210
- Proportion of subjects in each group with LDL-C greater than 80% of the baseline value at Day 180 and Day 210
- Duration of time on treatment for subjects to return to 80% of baseline or greater LDL-C or PCSK9 protein
- Individual responsiveness defined as the number of subjects reaching on treatment LDL-C levels of <25 mg/dL, <50 mg/dL, <70 mg/dL, and <100 mg/dL at Days 90, 120, and 180
- Proportion of subjects in each group with greater or equal to 50% LDL-C reduction from baseline at Days 90, 120, and 180
- Percentage change in PCSK9 levels from baseline to Days 14, 30, 60, 90, 104, 120, 150, 180, and 210
- Percentage change in other lipids, lipoproteins, apolipoproteins from baseline at each subsequent visit to Day 210

- Proportion of subjects in each group who attain global lipid modification targets for their level of ASCVD risk

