6.5. Follow-Up Visits 1 to 9(Day 14 to Day 210)

Subjects will return to the study center 14 days (\pm 2 days) after study drug administration for Follow-Up Visit 1, 30 days (\pm 3 days) after study drug administration for Follow-Up Visit 2, and monthly (\pm 3 days) after that for Follow-Up Visits 3 to 7. The following procedures will be performed at these visits:

- Vital signs: blood pressure, heart rate, temperature, and respiration will be measured at each visit. For subjects who receive a second dose of study drug, vital signs will be measured prior to injection and at 4 hours after injection
- HbA1c: At Day 90 and Day 180 (central)
- Central clinical laboratory (hematology, chemistry [including fasting glucose, liver and renal function, hsCRP and inflammatory markers IL6, IFN- γ and TNF- α], and coagulation testing)
- ADA: at Day 30, Day 60, Day 90, Day 120, Day 150, and Day 180 (Note: Day 150 and Day 180 only in subjects who receive a second dose of study drug. An additional blood draw for ADA testing at Day 60, Day 90, Day 150, and Day 180 is not required; a stored serum sample will be used.) (central)
- Central laboratory for efficacy parameters (lipid panel, LDL-C by beta quantification, PCSK9, hsCRP, lipoprotein a [Lp(a)], apolipoprotein A1 [Apo-A1] and apolipoprotein B [Apo-B])
- Study drug administration: Second dose at Follow-Up Visit 4 (Day 90) for subjects randomized to receive two doses
- Pregnancy test (local; women of childbearing potential only): At Day 14 and monthly beginning at Day 30 through Day 180
- Concomitant medications
- AE reporting
- SAE reporting

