6.7. Additional Follow-Up Visits (Day 240 to Day 360)

Subjects in whom LDL-C levels have not returned to >80% of baseline values will return monthly (± 3 days) for Follow-Up Visits 10 to 14 (Days 240, 270, 300, 330, and 360) either until this level has been reached or until Day 360. The following procedures will be performed at these visits:

- HbA1c: At Day 270 and Day 360 (central)
- Central clinical laboratory (hematology, chemistry [including fasting glucose, liver and renal function, hsCRP and inflammatory markers IL6, IFN- γ and TNF- α], and coagulation testing)
- ADA at the last visit(central)
- Lipids/lipoproteins (LDL-C, HDL-C, total cholesterol, triglycerides) and PCSK9; non-HDL-C and very low-density lipoprotein-cholesterol [VLDL-C] will be derived from the lipid panel (central)
- Pregnancy test (local) at each additional follow-up visit until LDL-C has returned to > 80% of baseline values
- Concomitant medications

- AE reporting
- SAE reporting

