10.3.2.2. Modified Intent-to-Treat (mITT) Population

All randomized subjects who receive at least one dose of study drug and have both the baseline and the 180 day follow-up LDL-C assessment. Treatment classification will be based on the randomized treatment. This will be the primary population for analysis of the primary and secondary endpoints.

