10.3.3. Analysis Windows and Baseline

The observational period for each subject includes the screening period (from Day -14 to Day -1), the EOS visit (Day 210 or withdrawal date). The time at which LDL-C levels have returned to >80% of baseline values will be the last observation. Any lab results collected after the last observation will not be included in the planned efficacy analysis. Safety events after the last observation, even if collected on the eCRF, will not be included in the planned statistical analysis. However, all data, including that reported after the defined observational period, will be included in the subject data listings.

Unless otherwise specified, for evaluations that are collected at multiple occasions prior to initiation of study drug, the last evaluation will be considered the "Baseline" evaluation for analysis.

Two samples for lipids and PCSK9 will be taken prior to initiation of study drug (one at screening and one prior to randomization on Day 1). The average value of the two samples will be used as the baseline evaluation.

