10.3.4. Missing Data Handling

Unless otherwise specified, missing data will not be imputed and will be excluded from the associated analysis.

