5.3. General Statistical Considerations and Definitions

5.3.1. General Statistical Methods

All study-collected data will be summarized by treatment group using descriptive statistics, graphs, and/or raw data listings. Categorical variables will be summarized using counts and percentages. Percentages are based on the number of subjects in the analysis set for whom there are non-missing data, unless otherwise specified. Continuous variables, including changes from baseline, will be summarized using descriptive statistics (n, mean, standard deviation [SD], confidence intervals, median and interquartile range [Q1 and Q3], minimum and maximum).

The Statistical Analysis Plan (SAP) will be finalized before database lock.

Statistical analyses will be carried out using SAS statistical analysis software version 9.2 or higher (SAS Institute, Inc., Cary, North Carolina, USA).

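### Time for LDL-C to return to 80% of baseline is right-censored, but only generic summary rules apply to it; as written they shorten duration most in the longest-acting regimens

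*Protocol*

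**What the plan says.** The endpoint appears in Protocol sections 3.4, 7.2.1 and 10.4.3.2 and in SAP section 5.4.4.2. The protocol wording is "Duration of time on treatment for subjects to return to 80% of baseline or greater LDL-C or PCSK9 protein". The SAP repeats it, changes the threshold to above 80%, and adds that unresolved subjects are followed until return, with no upper limit. None of these sections names an estimator or says how to treat a subject who has not returned.

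The rules that apply by default are general ones:

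- Protocol synopsis: "The analysis of the secondary and exploratory endpoints will be descriptive".
- SAP 5.3.1 (and Protocol 10.3.1): "Continuous variables, including changes from baseline, will be summarized using descriptive statistics", meaning n, mean, SD, median, quartiles and range; the SAP adds confidence intervals.
- Protocol 10.3.4 (and SAP 5.3.4): "missing data will not be imputed and will be excluded from the associated analysis".
- Protocol 10.3.2.2 (and SAP 5.3.2.2): the primary population for secondary endpoints must "have both the baseline and the 180 day follow-up LDL-C assessment".

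On follow-up, Protocol 6.7 brings unreturned subjects back monthly "either until this level has been reached or until Day 360". Protocol section 6 and a footnote to SAP Table 2 give the same limit. Protocol 10.3.3 (and SAP 5.3.3) adds "The time at which LDL-C levels have returned to >80% of baseline values will be the last observation" and keeps later laboratory results out of the efficacy analysis. SAP section 7 declares no change from the protocol.

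**The concern.** A subject below 80% of baseline at the last sample has a duration known only to exceed that day. A plain mean or median has no place for such a value, so an analyst applying the general rules would naturally summarise those who returned. Subjects without a Day 180 LDL-C drop out of the population altogether, although a subject who leaves on Day 150 still suppressed carries information.

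The subjects lost this way are those with the longest effect, so the loss is greatest in the longest-acting regimens and differences between regimens shrink. Duration of lipid lowering by dose is a stated secondary objective (Protocol 2.2), and the results are to help choose later doses (Protocol 1.3.1, SAP 5.4.4). The five visits from Day 240 to Day 360 exist to observe late return, yet no estimate is specified for them.

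The last-observation sentence is a second problem. A placebo subject will often be above 80% of baseline at the first follow-up visit. Read literally, that visit is the subject's last observation, and every later LDL-C value, including Day 180, leaves the efficacy analysis.

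**Working it through.** The plan states no figure for this endpoint, so there is none to reproduce. The follow-up limit is consistent with the stated durations: 14 + 210 = 224 days and 14 + 360 = 374 days.

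**Direction, without a distribution.** Let P be the share returned by Day 360, with exact times and no earlier withdrawal. The median among returners is the P/2 quantile of all return times, not the 1/2 quantile. With 10%, 30% or 50% unreturned, it is the 45th, 35th or 25th percentile. It cannot exceed the true median, and it falls further as more subjects stay suppressed.

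**Is non-return plausible?** Inputs from Phase I: mean nadir reduction 50 to 59% at 300 mg or higher, maximum effect by Day 84 (Protocol 1.3.2), and about 40% reduction at Day 140 (Protocol 1.2.2). Assume the nadir falls at Day 84 and extrapolate to a 20% reduction:

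- Linear: 140 + 20/((nadir − 40)/56) = Day 252 (nadir 50) or Day 199 (nadir 59).
- Exponential: 140 + ln 2/(ln(nadir/40)/56) = Day 314 or Day 240.

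The one-dose range is therefore Day 199 to 314. If the second injection restarts the course (assumption), adding 90 gives Day 289 to 404.

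**Share unreturned and returner-only median.** Assume log-normal times with median m and log-SD s = 0.3. Then P = Φ(ln(360/m)/s), and the returner-only median is m·exp(s·Φ⁻¹(P/2)).

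| m | unreturned at Day 360 | returner-only median |
|---|---|---|
| 199 | 2.4% | 197.2 |
| 314 | 32.4% | 277.0 |
| 289 | 23.2% | 264.5 |
| 404 | 65.0% | 305.3 |

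For s from 0.2 to 0.4, the unreturned share spans 0.2 to 37% (one dose) and 14 to 72% (two doses).

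**On the actual visit schedule.** Recorded return is the first visit at or after true return, which pushes recorded times later and partly offsets the bias. Simulated arms of 60, s = 0.3, 15% withdrawal by Day 180 continuing at the same rate (the 15% is from Protocol 10.1; its timing is assumed), Day 180 value required; typical arm medians:

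| true median | returners only | Kaplan-Meier |
|---|---|---|
| 195.5 | 210 | 210 |
| 255 | 255 | 270 |
| 345 | 300 | 360 (not reached in 22% of arms) |

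Regimens whose true medians are 345 − 255 = 90 days apart show 300 − 255 = 45 days apart among returners, and 360 − 270 = 90 by Kaplan-Meier.

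**PCSK9.** Protocol 6.5 samples every subject at each visit ("Central laboratory for efficacy parameters (lipid panel, LDL-C by beta quantification, PCSK9, hsCRP"), and section 6.6 does so at Day 210. Only from Day 240 does PCSK9 sampling depend on LDL-C (6.7), so proportions at fixed visits through Day 210 are sound.

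**The case against.** The strongest reply is that the harm is conditional. A reader might infer that the plan orders non-returners to be excluded. It does not: no section says that non-return counts as missing, a subject measured below 80% at Day 360 has been observed, and a descriptive analysis may include Kaplan-Meier curves. That stands. Exclusion is what the general rules lead to, not a stated rule.

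A reader might also infer that the endpoint has no time origin. Protocol section 6 places initiation of study drug on Day 1, so time on treatment naturally runs from Day 1. What remains open is the two-dose subject who has already returned by the second injection; counting from Day 90 instead shifts a time by 89 days.

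The figures are fragile. The 50 to 59% nadir is for 300 mg or higher, while three of the six regimens use 100 or 200 mg; the doses behind the Day 140 figure are not given. Visit-to-visit LDL-C variation brings the first crossing forward. At a median of 314 with exponential decay from 50%, variation of 10% or 15% cuts the unreturned share from 32% to 16% or 9%, and the returner-only and all-subject medians then coincide on the visit schedule (270 and 240). This stands as a limit on size, not on direction.

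The Day 180 requirement adds little by itself: Protocol 4.4 asks for follow-up sampling regardless of treatment, and removing withdrawals biases the result only if withdrawal is related to duration.

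Finally, the proportions above 80% at Days 180 and 210 and the changes by visit describe durability without this difficulty. True, but only through Day 210.

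**Conclusion.** The point holds as a gap with a known direction and an unknown size. The endpoint is right-censored by design. The rules that apply would, followed as written, leave still-suppressed subjects without a duration and remove those lacking a Day 180 value. The bias is toward short durations and is largest in the longest-acting regimens. It is negligible if nearly all subjects return by Day 360. The figures in days rest on assumed distributions and a rough Phase I extrapolation; they are not estimates for this trial.

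The last-observation sentence needs correcting in its own right. A reader might infer that the sponsor intends to discard Day 180 LDL-C for placebo subjects. The documents do not support that: Day 180 LDL-C is the primary endpoint, and Protocol sections 6 and 6.7 apply the return rule to follow-up after Day 210. The sentence is probably a drafting slip, but it sits in the section that defines which data are analysed.

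The stake is moderate: one untested secondary summary that bears on a stated objective and on dose choice. The change should be made before database lock.

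**What to change.** In SAP 5.4.4.2, with the departure from the mITT set recorded in SAP section 7:

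- Measure time from Day 1. Estimate it per regimen by Kaplan-Meier or interval-censored methods in all dosed subjects with a baseline LDL-C. Censor unreturned subjects at their last LDL-C sample, at most Day 360.
- Use one threshold throughout. Protocol 3.4 counts a value of exactly 80% as return, whereas Protocol 6.7 and 10.3.3 and SAP 5.4.4.2 require more than 80%.
- State how two-dose subjects who return at or before the Day 90 injection are counted, for example by also reporting time from last injection.
- Report subjects never below the threshold separately, outside the curve.
- Give the median with confidence interval, or state that it was not reached, and the number censored.
- For PCSK9, report proportions returned at fixed visits through Day 210.

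In SAP 5.3.3, with the matching clarification of Protocol 10.3.3, confine the last-observation sentence to the additional follow-up after Day 210, so that no scheduled sample through Day 210 is dropped. Reconcile the uncapped follow-up wording in SAP 5.4.4.2 with the Day 360 limit in Protocol section 6 and the SAP Table 2 footnote.

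The cost is SAP text, one additional survival output and the section 7 entry. No new visits or data are needed.

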3.5. Exploratory Endpoint(s)

The exploratory endpoints of this trial are:

- CV events such as CV death, non-fatal MI, resuscitated cardiac arrest, and non-fatal stroke (ischemic and hemorrhagic)
- Evaluation of ADA for the investigational product

3.6. Measures to Minimize/Avoid Bias

3.6.1. Blinded Study Where Pharmacist is Unblinded

The study will be conducted using a double-blind design, with placebo matched by volume within each dose and regimen but not between regimens. Specifics on how the blind for the study drug is maintained are provided in [Section 5.4.1](#). Allocation of treatment is not disclosed to the study team. Study medication will be prepared by the unblinded hospital pharmacist and will be dispensed in a blinded syringe as randomized by the interactive web response system (IWRS). Pharmacists will be required by signature to keep the study personnel blinded. Blinding is achieved by placing an over label on each unique syringe dispensed by the pharmacist. The over label will cover the outside of the syringe masking the color of the solution within.

4. SUBJECT POPULATION

4.1. Number of Subjects

This will be a multi-center study conducted in North America and Europe. A total of 480 randomized subjects are planned for inclusion in the study: 60 subjects per each of six ALN-PCSSC treatment groups plus 120 subjects total across the placebo groups (20 subjects each to match each of the six drug groups). Assuming about a 15% drop out rate, the sample size will be approximately 100 evaluable subjects total across the placebo groups and approximately 50 subjects in each of six ALN-PCSSC treatment groups. This sample size of at least 400 evaluable subjects will provide more than 90% power to detect a 30% reduction of LDL-C levels in at least one ALN-PCSSC dose group.

4.2. Inclusion Criteria

Subjects may be included in the study if they meet all of the following criteria:

1. Male or female subjects ≥ 18 years of age.
2. History of ASCVD or ASCVD-risk equivalents (symptomatic atherosclerosis, Type 2 diabetes, familial hypercholesterolemia, including subjects whose 10-year risk of a cardiovascular [CV] event assessed by Framingham Risk Score* or equivalent has a target LDL-C of < 100 mg/dL).
3. Serum LDL-C ≥ 1.8 mmol/L (≥ 70 mg/dL) for ASCVD subjects or ≥ 2.6 mmol/L (≥ 100 mg/dL) for ASCVD-risk equivalent subjects at screening.
4. Fasting triglyceride < 4.52 mmol/L (< 400 mg/dL) at screening.
5. Calculated glomerular filtration rate > 30 mL/min by estimated glomerular filtration rate (eGFR) using standardized local clinical methodology.
6. Subjects on statins should be receiving a maximally tolerated dose (investigator's discretion).
7. Subjects on lipid-lower therapies (such as statin and/or ezetimibe) should be on a stable dose for ≥ 30 days before screening with no planned medication or dose change during study participation.
8. Willing and able to give written and informed consent before initiation of any study-related procedures and willing to comply with all required study procedures.

*By Framingham Risk Score $> 20\%$

4.3. Exclusion Criteria

Subjects will be excluded from the study if any of the following exclusion criteria apply immediately prior to randomization:

1. Any uncontrolled or serious disease, or any medical or surgical condition, that may either interfere with participation in the clinical study, and/or put the subject at significant risk

(according to investigator's [or delegate] judgment) if he/she participates in the clinical study.

2. An underlying known disease, or surgical, physical, or medical condition that, in the opinion of the investigator (or delegate) might interfere with interpretation of the clinical study results.
3. New York Heart Association (NYHA) class II, III or IV heart failure or last known left ventricular ejection fraction <30%.
4. Cardiac arrhythmia within 3 months prior to randomization that is not controlled by medication or via ablation.
5. Any history of hemorrhagic stroke.
6. Major adverse cardiac event within 6 months prior to randomization.
7. Uncontrolled severe hypertension: systolic blood pressure >180 mmHg or diastolic blood pressure >110 mmHg prior to randomization despite anti-hypertensive therapy.
8. Poorly controlled Type 2 diabetes, ie, glycated hemoglobin A1c (HbA1c) >10.0% prior to randomization.
9. Active liver disease defined as any known current infectious, neoplastic, or metabolic pathology of the liver or unexplained ALT, aspartate aminotransferase (AST), elevation >2x ULN or total bilirubin elevation >1.5x ULN at screening confirmed by a repeat measurement at least 1 week apart.
10. Serious comorbid disease in which the life expectancy of the subject is shorter than the duration of the trial (eg, acute systemic infection, cancer, or other serious illnesses). This includes all cancers with the exception of treated basal-cell carcinoma occurring >5 years before screening.
11. Females who are pregnant or nursing, or who are of childbearing potential and unwilling to use at least two methods of contraception (oral contraceptives, barrier methods, approved contraceptive implant, long- term injectable contraception, intrauterine device or tubal ligation)**. Women who are >2 years postmenopausal defined as ≥ 1 year since last menstrual period AND if <55 years old with a negative pregnancy test within 24 hours of randomization or surgically sterile are exempt from this exclusion.
12. Males who are unwilling to use an acceptable method of birth control during the entire study period (ie, condom with spermicide).
13. Known history of alcohol and/or drug abuse within the last 5 years.
14. Treatment with other investigational medicinal products or devices within 30 days or five half-lives, whichever is longer.
15. Use of other investigational medicinal products or devices during the course of the study.
16. Any condition that according to the investigator could interfere with the conduct of the study, such as but not limited to:
 - a. Inappropriate for this study, including subjects who are unable to communicate or to cooperate with the investigator

- b. Unable to understand the protocol requirements, instructions and study-related restrictions, the nature, scope, and possible consequences of the study (including subjects whose cooperation is doubtful due to drug abuse or alcohol dependency)
- c. Unlikely to comply with the protocol requirements, instructions, and study-related restrictions (eg, uncooperative attitude, inability to return for follow-up visits, and improbability of completing the study)
- d. Have any medical or surgical condition, which in the opinion of the investigator would put the subject at increased risk from participating in the study
- e. Involved with, or a relative of, someone directly involved in the conduct of the study
- f. Any known cognitive impairment (eg, Alzheimer's disease)

17. Previous or current treatment (within 90 days of screening) with monoclonal antibodies directed towards PCSK9.

**For the entire duration of the study

Subjects excluded for any of the above reasons may not be re-screened for participation at any time if the exclusion characteristic has changed.

